5.3.5 Efficacy Data Statistical Inference

5.3.5.1P-values

P-values will be reported out and rounded off to 4 numbers after the decimal point (i.e. "0.####). Any p-values that are > 0.9999 will be reported as ">.9999" in the tables. Any p-values that are < 0.0001 will be reported as "<.0001" in the tables.

5.3.5.2 Analysis of Covariance Model

Using the change from baseline as a dependent variable, an analysis of covariance (ANCOVA) model with treatment (200 mg of NYX-2925, 50 mg of NYX-2925, 10 mg of NYX-2925, and Placebo) as the main effect and the baseline value as a covariate will be used to compare treatment groups at an individual analysis visit^[4]. The comparison of the NYX-2925 versus placebo will be assessed by forming the least squares means estimate of each particular NYX-2925 treatment groups stated in Section 5.2 and comparing them to the placebo group. The Kenward-Roger approximation will be used to estimate denominator degrees of freedom. Here is the SAS® code:

PROC MIXED DATA=ADAM ORDER=DATA METHOD=REML;

CLASS TRTP;

MODEL CHG = BASE TRTP / DDFM=KENWARDROGER;

LSMEANS TRTP / DIFF CL ALPHA=0.05;

/* -1 = Placebo; 0 = 10 mg of NYX-2925; 0.5 = 200 mg and 50 mg of NYX-2925 */

LSMESTIMATE "200 mg and 50 mg of NYX-2925 versus Placebo" TRTP 0 0.5 0.5 -1 / CL;

RUN:

The following ANCOVA model statistics for each treatment group will be presented in an analysis table:

- n =the number of records for that treatment or pooled treatment group
- Least Squares Mean for the treatment groups
- Standard Error for the treatment groups
- Least Squares Mean Difference for the NYX-2925 treatment groups versus Placebo
- Standard Error Difference for the treatment groups versus Placebo
- 95% Confidence Interval for the Difference for the treatment groups versus Placebo
- P-value for the Difference for the treatment groups versus Placebo

5.3.5.3 Mixed Effects Repeated Measures Model

A mixed effects repeated measures (MMRM) model will be used for modeling analyses over time with each post-baseline analysis visit^[4]. The dependent variable will be the change from baseline and the model will include treatment (200 mg of NYX-2925, 50 mg of NYX-2925, 10 mg of NYX-2925, and Placebo), analysis visit, treatment-by-analysis visit interaction, the baseline value as a covariate, and subject as a random effect. The comparison of the NYX-2925 versus placebo will be assessed by forming the least squares means estimate of each particular NYX-2925 treatment groups stated in Section 5.2 and comparing them to the placebo group at each post-baseline analysis visit. An unstructured covariance structure will be used to model the within-subject errors. The Kenward-Roger approximation will be used to estimate denominator degrees of freedom. Here is the SAS® code:

PROC MIXED DATA=ADAM ORDER=DATA METHOD=REML;

CLASS USUBJID TRTP AVISITN:

MODEL CHG = BASE TRTP AVISITN TRTP*AVISITN / DDFM=KENWARDROGER;

REPEATED / TYPE=UN SUBJECT=USUBJID R;

LSMEANS TRTP*AVISITN / DIFF CL ALPHA=0.05;

RUN;

In case of convergence issues, other covariance structures will be used including (but not limited to) autoregressive (AR (1)), compound symmetry (CS), and variance components (VC) to find the covariance structure with the best fit. The fit statistics will be compared for all covariance structures; the structure with the smallest Akaike information criterion will be retained as the preferred model.

The following MMRM model statistics for each treatment group at every post-baseline analysis visit will be presented in an analysis table:

- n = the number of records for that treatment or pooled treatment group at that analysis visit
- Least Squares Mean for the treatment groups
- Standard Error for the treatment groups
- Least Squares Mean Difference for the NYX-2925 treatment groups versus Placebo
- Standard Error Difference for the treatment groups versus Placebo
- 95% Confidence Interval for the Difference for the treatment groups versus Placebo
- P-value for the Difference for the treatment groups versus Placebo

Each dependent variable and the particular analysis visit(s) will be described in the efficacy analyses Section 9 that will be used in a MMRM model.

5.3.5.4Time-to-Event Analyses

The post-baseline study day at which the pre-defined responder status occurs will be used in the analysis of number of days to responder status analyses. If a subject never reaches the pre-defined responder status then the number of days will be censored at Day 28 or the day of the last particular efficacy assessment, whichever is earliest. Number of days to responder status will be analyzed by the Cox proportional hazards model with the baseline mean NRS score pain intensity score of interest as a covariate^[4]. The adjusted hazard ratio, 95% CI, and a p-value will be provided from the model

for each NYX-2925 treatment groups versus Placebo. The n (%) of subjects who are considered a responder as well as the n (%) of censored observations will be presented for each treatment group. Here is the SAS® Code:

PROC PHREG DATA=ADAM:

CLASS TRTP;

MODEL AVAL*CNSR(1) = TRTP BASEPAIN / RISKLIMITS=WALD;

RUN;

Additionally, the Kaplan-Meier method will be analyzed for the probability plots only. The same censoring technique will be used as stated in the Cox proportional hazards model. Here is the SAS® Code:

PROC LIFETEST DATA=ADAM CONFTYPE=LINEAR METHOD=KM ALPHA=0.05;

TIME AVAL*CNSR(1);

STRATA TRTP;

RUN;

The specific number of days to responder statuses calculated will be described in Section 9.3.3 and the number of days to sustained pain reduction in Section 9.3.4 of the SAP.

5.3.5.5Frequency Distribution Tests

Frequency distributions that have two responses (i.e. yes/no) and compare two different treatment groups (i.e. active versus placebo) may use a chi-square test for reporting a p-value. This is referred to as a 2x2 table. If the expected cells counts for any of the 2x2 tables are not \geq 5, then Fisher's exact test will be used instead. Each p-value using Fisher's exact test will be denoted in any summary table.

Odds ratio and relative risk estimates will be provided when chi-square or Fisher's exact test p-values are reported in summary tables^[4]. Both the odds ratio and relative risk estimates will be based on the "yes" responders of the active treatment as the numerator compared to the placebo treatments as the denominator in these estimates. 95% confidence intervals will also be provided for both odds ratio and relative risk estimates. Here is the SAS® code:

PROC FREQ DATA=ADAM;

WEIGHT COUNT;

/* where # is based on the type of responder criterion in CRIT#FLN */

TABLES TRTP*CRIT#FLN / FISHER CHISQ RELRISK;

ODS OUTPUT Freq.Table1.RelativeRisks=ODDSRATIO(WHERE=(Statistic="Odds Ratio"));

ODS OUTPUT Freq.Table1.RelativeRisks=RELRISK(WHERE=(Statistic="Relative Risk (Column 1)"));

RUN;

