12.5.1.2 Sensitivity Analysis

For the primary efficacy endpoint, the daily pain intensity NRS score from the handheld device will be averaged for baseline (Days -7 to -1) and each week (Days 1 to 7, Days 8 to 14, Days 15 to 21, and Days 22 to 28) after randomization. A mixed model repeated measures analysis of variance will be used to assess treatment differences. The model will include factors for study site, treatment, week, and the treatment-by-week interaction, with baseline value as a covariate.

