4.4 Sample Size Considerations

The planned sample size is 75 randomized subjects per group for a total of 300 randomized subjects.

The mean and standard deviation for reduction in pain from baseline for placebo and active drug were estimated from publicly available sources on duloxetine, pregabalin, gabapentin, and oxycodone. The mean difference from placebo based on higher dose groups (duloxetine \geq 60 mg once daily and pregabalin \geq 300 mg) was estimated at 1.05. The standard deviation was estimated as 2.25.

A sample size of 75 subjects per group will provide approximately 80% power for a 2-sided t-test with Type I error of $0.05^{[5]}$ when the mean difference from placebo is 1.05 and the standard deviation is 2.25.

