5.6 Multiplicity Adjustments and Type I Error

No formal adjustments for multiplicity will be performed for this phase 2 study. All p-values will be tested using alpha at the 0.05 level, two-tailed.

As an exploratory procedure, multiple comparisons for the primary endpoint may be performed, using Hochberg's procedure^[6]. Only the individual NYX-2925 treatment arms versus Placebo would use this method. The Type I error would be set at 0.05. A nested testing procedure is used after the p-values are ranked from largest to smallest. These are the 3 steps that would be followed:

- Step 1: if the largest observed p-value is \leq 0.05, then statistical significance would be declared for all 3 comparisons.
- Step 2: if the largest observed p-value is > 0.05, then the remaining 2 comparisons would be tested against 0.05 / 2 = 0.025. If the second largest observed p-value is ≤ 0.025 , then statistical significance would be declared for the 2 smallest p-value comparisons.
- Step 3: if the second largest observed p-value is > 0.025, then the last comparison would be tested against 0.05 / 3 = 0.017. If the smallest observed p-value is ≤ 0.017 , then statistical significance would be declared only for the smallest p-value comparison.

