9.2.1 NRS Score Assessing Worst Pain Intensity in the Past 24 Hours

The collection method of the NRS score assessing worst^[10] pain intensity in the past 24 hours is the same as the primary efficacy data described in Section 9.1 for the NRS score assessing average pain intensity in the past 24 hours. The study-issued handheld devices were not programmed with logic checks to flag instances in which subjects might have mistakenly reported their worst pain intensity scores as being less than their average pain intensity scores. However, rather than assume these to be self-evident errors and thus correct them, such scores will be analyzed based on the actual values collected.

The secondary endpoints of interest with this data is the change in the mean score from baseline to each analysis week of treatment (Weeks 1, 2, 3, and 4). The same analyses methods will be applied to the NRS score assessing worst pain intensity in the past 24 hours as described in Sections 9.1, 9.1.1, and 9.1.2. No imputation methods for missing data will be applied for this secondary endpoint.

The actual means, change from baseline, and percent change from baseline will be summarized using descriptive statistics. ANCOVA analyses using the mean change from baseline will be provided for Weeks 1, 2, 3, and 4 as described in Section 5.3.5.2. A MMRM model will be analyzed for all post-baseline analysis visits (Weeks 1, 2, 3, and 4) for the mean change from baseline as described in Section 5.3.5.3.

9.2.2 Change in the Mean NRS Score Assessing Average Pain Intensity in the Past 24 Hours at Weeks 1, 2, 3, and 4

This is the same data described in Section 9.1 for the NRS score assessing average pain intensity in the past 24 hours. The secondary endpoints of interest with this data is the change in the mean score from baseline to each analysis week of treatment (Weeks 1, 2, and 3). The same analyses methods will be applied to Weeks 1, 2, and 3 as described in Section 9.1.2 for Week 4.

ANCOVA analyses using the mean change from baseline will be provided for individual models for Weeks 1, 2, and 3 as described in Section 5.3.5.2. A MMRM model will be analyzed for all postbaseline analysis visits (Weeks 1, 2, 3, and 4) for the mean change from baseline as described in Section 5.3.5.3. No imputation methods for missing data will be applied for the MMRM model.

9.2.3 NRS Score Assessing Average Pain upon Walking Intensity in the Past 24 Hours

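### The MMRM fits one baseline slope for all four weeks, so if slopes differ by week its Week 4 estimate can depart from the primary ANCOVA even with no missing data

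*SAP*

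**What the plan says.** SAP 5.3.5.3 gives the MMRM as "MODEL CHG = BASE TRTP AVISITN TRTP*AVISITN / DDFM=KENWARDROGER". On the covariance it says: "An unstructured covariance structure will be used to model the within-subject errors". Other structures come in only if the model does not converge. The SAP text, like the code, names baseline as a covariate without a baseline-by-visit term.

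Protocol 12.5.1.2 presents the MMRM as the sensitivity analysis of the primary endpoint: "The model will include factors for study site, treatment, week, and the treatment-by-week interaction, with baseline value as a covariate". SAP 4.7 later removes study site from every model, so site is not a source of difference between the MMRM and the ANCOVA.

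The ANCOVA in SAP 5.3.5.2 is "MODEL CHG = BASE TRTP / DDFM=KENWARDROGER" and "will be used to compare treatment groups at an individual analysis visit". Each week therefore has its own baseline slope. SAP 9.1.2 applies this model at Week 4 as the primary analysis.

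The MMRM is used for average pain (SAP 9.2.2), worst pain (9.2.1), walking pain (9.2.3) and DSIS (9.2.9). For worst pain, for example: "A MMRM model will be analyzed for all post-baseline analysis visits (Weeks 1, 2, 3, and 4").

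**The concern.** The two models adjust the same Week 4 data differently. The ANCOVA uses the Week 4 slope of change on baseline. The MMRM uses one slope estimated from all four weeks. If the slope changes over the weeks, as it may when change accumulates, the common slope is not the Week 4 slope.

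Two things follow. The Week 4 residual in the MMRM then carries some baseline variation that a Week 4 slope would have removed. And the two Week 4 treatment differences will not agree even if no diary data are missing. The second matters more for reading the results. The primary ANCOVA uses observed weekly means without imputation, so a reader who sets the two side by side will tend to take a gap as a signal about missing data. As specified, part of the gap can come from the baseline adjustment.

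**Working it through.** **The plan's own figure.** SAP 4.4 says: "A sample size of 75 subjects per group will provide approximately 80% power for a 2-sided t-test with Type I error of" 0.05, for a difference of 1.05 and an SD of 2.25. The standard error is 2.25 × √(2/75) = 0.367. Then 1.05/0.367 = 2.858, and 2.858 − 1.960 = 0.898, which gives 81.5% (81.0% with the t distribution). The figure reproduces.

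**Formulas, complete data.** Let b_t be the slope of change on baseline at week t, Σ the residual covariance of the four weeks, and D the difference in mean baseline between two arms. Treatment by week is saturated, so:

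- ANCOVA difference at Week 4 = difference in mean change − b4 × D.
- MMRM difference at Week 4 = difference in mean change − bc × D, where bc = Σ w_t b_t and w = Σ⁻¹1 / (1′Σ⁻¹1).
- Gap (MMRM − ANCOVA) = (b4 − bc) × D.
- Week 4 residual variance in the MMRM = s44 + Var(baseline) × (b4 − bc)², where s44 is the ANCOVA residual variance.

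Randomisation gives D a mean of zero, so neither estimate is biased.

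**Inputs.** From the SAP: 75 per arm and an SD of change of 2.25. Assumed, because the documents do not give them: baseline SD 1.3; slopes from -0.10 at Week 1 to -0.40 at Week 4 (steeper set) or from -0.15 to -0.30 (gentler set); residual SD flat, mildly rising (1.6 to 2.15) or clearly rising (1.2 to 2.2); between-week correlation 0.6 to 0.9, autoregressive (AR) or compound symmetric (CS). No dropout was modelled.

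**Weights.** With flat SD, CS gives each week 0.25. AR gives weights proportional to (1, 1−ρ, 1−ρ, 1), so at ρ = 0.9 Weeks 1 and 4 each get 1/2.2 = 0.45. The Week 1 weight is 0.60 to 1.15 with a mild rise in SD and 0.88 to 1.51 with a clear rise. A weight above 1 puts the common slope near or beyond the Week 1 slope.

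**Results.** s44 = 2.25² − 0.40² × 1.3² = 4.792 for the steeper set, and 2.25² − 0.30² × 1.3² = 4.910 for the gentler set. The SD of D is 1.3 × √(2/75) = 0.2123. The variance increase is 1.69 × (b4 − bc)² / s44, and the gap SD is 0.2123 × |b4 − bc|.

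| Residual SD, correlation | Slopes | bc | b4 − bc | Week 4 variance increase | Gap SD (NRS) |
|---|---|---|---|---|---|
| Flat, AR 0.9 | gentler | -0.227 | -0.073 | 0.2% | 0.016 |
| Flat, CS | steeper | -0.260 | -0.140 | 0.7% | 0.030 |
| Flat, AR 0.9 | steeper | -0.252 | -0.148 | 0.8% | 0.031 |
| Mild rise, CS 0.6 | gentler | -0.186 | -0.114 | 0.4% | 0.024 |
| Mild rise, AR 0.9 | steeper | -0.098 | -0.302 | 3.2% | 0.064 |
| Clear rise, AR 0.9 | steeper | -0.021 | -0.379 | 5.1% | 0.080 |
| Clear rise, CS 0.8 | steeper | 0.006 | -0.406 | 5.8% | 0.086 |
| Any, equal slopes | -0.30 throughout | -0.300 | 0 | 0 | 0 |

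For the steeper set the ANCOVA power is 83.6%. The MMRM has 83.3% in the flat rows and 81.5% in the worst row.

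**Simulation check.** In 3000 complete-data trials per scenario with 75 per arm, the gap SD was 0.03 to 0.08 for the steeper slopes. With equal true slopes it was 0.02, from sampling error in the slopes alone, and the standard error ratio was 0.997 to 0.999. Mean error was 0.005 or less for both estimates. An extreme corner (slopes -0.05 to -0.50, baseline SD 1.6, clear rise, AR 0.9) raises the Week 4 standard error by 8.8%.

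**With `BASE*AVISITN` added.** Every week then has the same regressors. With unstructured covariance and complete data, the Week 4 MMRM estimate equals the ANCOVA estimate: gap 0, standard error ratio 1.000.

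**The case against.** The model is prespecified, and the protocol and SAP agree on a baseline main effect, so there is no contradiction between them on this term. The primary result rests on the Week 4 ANCOVA, which this does not touch. SAP 9.1.3, the section on sensitivity analyses of the primary endpoint, relies on multiple imputation, LOCF and BOCF; the MMRM sits under the secondary endpoints in 9.2.2, and its tables are not marked for the topline. For worst pain, walking pain and DSIS it is one secondary analysis beside weekly ANCOVAs. The gap is also small: an SD of 0.08 is about a fifth of the planning standard error of 0.367, against a planned effect of 1.05.

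All of this stands and limits the weight of the point. It does not remove it. The protocol still names the MMRM as the primary endpoint's sensitivity analysis, and SAP section 13 lists its tables (14.2.1.3.1 and 14.2.1.3.2) under primary efficacy data.

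A reader might infer more than the documents support:

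- That Week 4 is adjusted with roughly the Week 1 slope. That needs residual SD that rises over the weeks. With flat SD, or under the compound-symmetry fallback, the common slope is an average or an equal mix of Weeks 1 and 4.
- That precision is certainly lost. That needs true slopes that differ by week.
- That the loss can be counted in subjects. The sample size was set for a two-group t-test, and the MMRM does not enter it.

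**Conclusion.** The point holds as a minor, conditional weakness of a supporting analysis. The single baseline slope is plain in the code and text. If the true slopes differ by week, the Week 4 MMRM estimate departs from the ANCOVA through chance baseline imbalance, without any missing data, and is slightly less precise.

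Under the assumed baseline SD of 1.3 and slopes steepening to -0.30 or -0.40, the Week 4 variance rises by about 0.2% to 0.8% with flat residual SD. With rising SD it rises by about 0.4% to 5%, and one combination in the grid reaches 5.8%. The gap SD is about 0.02 to 0.08 NRS points. With equal slopes there is no loss of precision. These sizes rest on inputs absent from the documents, so the existence of the gap is firmer than its magnitude.

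It would be wrong to conclude that the primary analysis is biased or weakened. The ANCOVA is unaffected, and with complete data both estimates are unbiased.

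**What to change.** In SAP 5.3.5.3, add `BASE*AVISITN` to the MODEL statement and name the baseline-by-visit interaction in the accompanying text. Apply it to every endpoint with an MMRM: average, worst and walking pain, and DSIS. Record it in SAP 4.7 as a change from the protocol's model.

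With unstructured covariance, the complete-data MMRM then reproduces the Week 4 ANCOVA estimate, so a remaining gap can be read as an effect of missing data. If a fallback covariance structure is used, its pooled variance can still make the standard errors differ.

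The cost is one model term, 3 degrees of freedom and a wording change in the SAP. If the slopes are in fact equal, the simulated standard error ratios of 0.997 to 0.999 put the price at 0.3% of the standard error or less. This is a cheap improvement, not a condition for the primary analysis to stand.

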9.1 Primary Efficacy Data

The primary efficacy data for this study is the NRS score assessing average pain intensity in the past 24 hours. Daily collected pain scores are based on an 11-point numerical rating scale/Likert scale ranging from 0 to 10. Where 0 represents no pain and 10 is the worst pain imaginable^[2].

The mean NRS score assessing average pain intensity in the past 24 hours will be calculated for the analysis visits described in Section 5.4.2^[4]:

- Baseline (average of Study Days -7 to -1)
- Week 1 (average of Study Days 1 to 7)
- Week 2 (average of Study Days 8 to 14)
- Week 3 (average of Study Days 15 to 21)
- Week 4 (average of Study Days 22 to 28)

The mean baseline visit will be calculated if at least 6 of the study days have a reported pain score. This is a requirement in order to be eligible for being randomized to a study drug treatment arm. There will need to at least 4 daily pain scores collected within a post-baseline analysis visit in order to calculate the mean pain score for that visit.

Each mean analysis visit score will take on values ranging from 0 to 10 and will be rounded off by one number after the decimal point. Data prior to Study Day -7 or after Study Day 28 will not be used in the mean calculated scores. No missing data imputations will be used for these observed means, but Section 9.1.3 will explain imputation methods used for sensitivity analyses.

The actual means, change from baseline, and percent change from baseline at each analysis visit will be summarized using descriptive statistics. The same descriptive statistics table will be additionally provided by each study site, age groups, gender, race, ethnicity, and subjects using or not using at least 1 concomitant analgesic medication at Baseline. All data collected and derived will be presented in subject listings.

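### The MMRM code names no visit effect in its REPEATED statement, so weeks can be misaligned for subjects with an intermittent gap unless blank rows are kept, and the text adds a random effect that the code does not fit

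*SAP*

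**What the plan says.** Protocol 12.5.1.2 names the repeated-measures model as the sensitivity analysis of the primary endpoint: "A mixed model repeated measures analysis of variance will be used to assess treatment differences". SAP 5.3.5.3 gives the details. On covariance it says "An unstructured covariance structure will be used to model the within-subject errors". Its list of model terms ends with "the baseline value as a covariate, and subject as a random effect".

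The code in the same section has three relevant lines:

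- "CLASS USUBJID TRTP AVISITN"
- "MODEL CHG = BASE TRTP AVISITN TRTP*AVISITN / DDFM=KENWARDROGER"
- "REPEATED / TYPE=UN SUBJECT=USUBJID R"

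Visit is therefore a class variable and part of the mean model, but it is not named as the repeated effect. There is no RANDOM statement. If the model fails to converge, the fallback structures include AR(1), compound symmetry and variance components, chosen by AIC.

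SAP 9.1 sets the rule for a weekly mean: "There will need to at least 4 daily pain scores collected within a post-baseline analysis visit in order to calculate the mean pain score". SAP 5.1.5 leaves the change score unreported when that mean is missing, and SAP 9.2.2 rules out imputation before the MMRM. The same model is applied to worst pain (9.2.1), walking pain (9.2.3) and DSIS (9.2.9).

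**The concern.** An unstructured matrix has a separate variance for each week and a separate covariance for each pair of weeks, so the software must know which week each row belongs to. With no repeated effect named, the only link is the row's position within the subject. Under the 4-day rule a subject can have Weeks 1, 3 and 4 but no Week 2. If that subject contributes three rows, Week 3 sits in the second slot and Week 4 in the third.

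The MMRM would then differ from the primary ANCOVA partly because of row order, and a reader could take that difference for sensitivity to missing data.

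The random-effect phrase is a separate defect and does not depend on the dataset: the text and the code describe different models.

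**Working it through.** **Software assumption.** PROC MIXED assigns rows to the covariance matrix by position when no repeated effect is named, and a row with blank CHG still holds its place. The documents do not state this.

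**Scale.** The plan gives no figure for the MMRM. The nearest is the sample-size statement in SAP 4.4: 75 per arm, difference 1.05, SD 2.25, two-sided 0.05. The standard error is 2.25 × √(2/75) = 0.367, and the exact noncentral t gives 81.0% power, so the stated 80% is reproduced. That calculation is for a t-test and is not affected by this point.

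**What goes wrong for one subject.** Take a subject with Weeks 1, 3 and 4 and no row for Week 2. The SDs (1.3, 1.8, 2.05, 2.25) and correlations are assumed.

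| Quantity | Right value | Value in the slot used by position |
|---|---|---|
| Week 3 SD | 2.05 | 1.80 (Week 2) |
| Week 4 SD | 2.25 | 2.05 (Week 3) |
| Weeks 1 and 3, correlation | 0.65 | 0.80 (Weeks 1 and 2) |
| Weeks 1 and 4, correlation | 0.55 | 0.65 (Weeks 1 and 3) |
| Weeks 3 and 4, correlation | 0.88 | 0.85 (Weeks 2 and 3) |

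The Week 4 value is given too small a variance, so it gets too much weight and counts as more precise than it is.

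**Simulation.** Each trial had 4 arms of 75 and 4 weeks, with the SDs above, correlations from 0.55 to 0.88 and 10% monotone dropout. Each week before a subject's last had a 0%, 3% or 10% chance of being a gap, with its row omitted. The documents give no dropout or gap rate, so these are assumptions. There were 150 trials per setting under no treatment effect.

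The fit was REML with an unstructured 4 × 4 matrix Σ. For subject i, V_i = Σ[s_i, s_i], where s_i is either the weeks observed (by visit) or 1, …, n_i (by position). Then β = (Σ X_i′V_i⁻¹X_i)⁻¹ Σ X_i′V_i⁻¹y_i, and the standard error comes from the inverse of the first sum. Tests used ±1.96 without the Kenward-Roger correction.

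*Share of subjects shifted, by hand.* At a 10% gap chance, completers give 1 − 0.9³ = 27.1%. Dropouts give the average of 0%, 10% and 19%, which is 9.7%. Overall: 0.9 × 27.1 + 0.1 × 9.7 = 25.4%, against 25.5% simulated.

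| Week 4 active minus placebo | No gaps | 3% per week | 10% per week |
|---|---|---|---|
| Subjects shifted | 0% | 8.2% | 25.5% |
| Mean absolute change in estimate | 0 | 0.050 | 0.086 |
| Largest change in a trial | 0 | 0.19 | 0.40 |
| Mean SE, by visit | 0.375 | 0.3767 | 0.3741 |
| Mean SE, by position | 0.375 | 0.3734 | 0.3642 |
| Empirical SD, by visit | 0.419 | 0.4173 | 0.3679 |
| Empirical SD, by position | 0.419 | 0.4213 | 0.3786 |
| Null rejection, by visit / by position | 7.3% / 7.3% | 7.3% / 6.7% | 4.7% / 5.3% |

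The SE is too small by 1 − 0.3734/0.3767 = 0.9% and 1 − 0.3642/0.3741 = 2.6%. The mean shift is 0.050/0.377 = 13% and 0.086/0.374 = 23% of a standard error. Mean estimates stayed within 0.03 of zero under both fits. Monte Carlo error on a rejection rate near 5% is √(0.05 × 0.95/150) = 1.8 points, so the rejection rates do not separate the fits. With dropout only and no gaps, the two fits are identical.

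**Random effect.** A random subject intercept with variance τ² gives V = R + τ²J, where J is all ones. With four weeks, an unstructured R already has 4 variances and 6 covariances, 10 in all, one for each distinct element of V. Adding τ² makes 11 parameters for 10 elements, so τ² cannot be estimated separately.

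**The case against.** The strongest objection is that the misalignment is conditional. A reader might infer that every subject with a gap week is misfitted by this code. The documents do not support that: if ADAM carries a blank row in visit order for each missing week, position and week agree. The SAP points both ways. SAP 5.3.5.3 reports n as a count of records per visit, which suggests absent rows. SAP 5.1.3 speaks of a not-reported record when a value cannot be calculated, which suggests blank ones, though in the context of displays. The dataset name in the code is a placeholder used across several procedures. This objection stands and sets the limits of the point.

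A reader might also infer that ordinary dropouts are mishandled. They are not: when the missing weeks are all at the end, the remaining rows stay aligned. Compound symmetry and variance components do not depend on position either. AR(1) would be affected.

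Gaps may also be rare. One needs at least 4 of 7 diary days missed, then a return to adequate reporting. Randomization required at least 6 baseline days (SAP 9.1), and sites reinforce diary completion by telephone and at visits. This is fair: no gap rate is given, and 10% per week may be high.

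Finally, the MMRM carries limited weight. It is the only sensitivity analysis named in protocol 12.5.1.2, but protocol 12.3 leaves missing-data procedures to the SAP, and SAP 9.1.3 adds multiple imputation, LOCF and BOCF. No MMRM table is marked for the topline, and SAP 5.6 plans no formal multiplicity control. This lowers the severity. It does not justify leaving pre-specified code whose correctness rests on an unstated dataset layout.

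On the random effect, the code shows which model would be run, so the discrepancy is mainly one of wording. It still needs correcting, because a programmer working from the text would fit an over-parameterised model.

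**Conclusion.** The point holds in conditional form, with low-to-moderate severity. The code leaves the link between row and week to dataset layout, and the SAP does not fix that layout. If gap rows are absent or rows are unsorted, the MMRM for average pain, worst pain, walking pain and DSIS uses the wrong week's variance and correlation for the subjects concerned.

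Under the assumed inputs the cost is modest. The Week 4 difference moves by about 0.05 to 0.09 NRS points on average, and by up to 0.40 in a single simulated trial. The standard error is understated by about 1% to 3%, while the estimate becomes slightly noisier. No bias was visible and no inflation of the error rate was shown. The sizes depend on assumed SDs, correlations, dropout and gap rates, and on the stated reading of PROC MIXED.

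It would be wrong to conclude that the MMRM results are invalid as coded, or that the primary result is in doubt. The primary Week 4 ANCOVA is a single-visit model and does not use this statement.

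The mismatch between text and code over the random effect holds whatever the layout.

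**What to change.** In SAP 5.3.5.3, write the statement as `REPEATED AVISITN / TYPE=UN SUBJECT=USUBJID R;`. Each row is then tied to its own week whether or not blank rows are present, and the same line works for AR(1) if that fallback is needed. Stating that the dataset holds one sorted row per subject per week, blank weeks included, would also serve, but it is easier to break.

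Delete the mention of subject as a random effect from the model description.

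The cost is one word of code and one phrase of text. Sample size, data collection and the primary analysis do not change.
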